- Group B: Trial subjects in either the trial BNT162-01 or BNT162-04 who did not receive the full two vaccinations of 30 µg Comirnaty will be offered two injections of 30 µg Comirnaty as per the conditional marketing authorization. Day 1 (baseline in this trial) must occur ≥12 weeks after receiving the last BNT162 candidate vaccine in the BNT162-01 or BNT162-04 trial.

*Group A excludes transplant subjects from Cohort 13 of the BNT162-01 trial; consenting transplant subjects will enroll into Group B immunology subgroup and will receive one injection, which will be followed 3 to 7 months afterward by a second injection of Comirnaty. Henceforth this group is referred to as Group B transplants.

All potential rollover volunteers must enroll in this trial within less than 18 months of their last injection of a BNT162 candidate vaccine in the parent BNT162-01 or BNT162-04 trials.

BNT162-01 or BNT162-04 trial subjects, including trial subjects who are still in the followup phase of their parent trial, will be actively informed about this rollover trial once it has received all necessary regulatory and ethical approvals. Depending on the timing of followup in the parent trial, data from the parent trial may be used to determine eligibility in this rollover trial after the trial subject has consented. Once the trial subject has enrolled into this rollover trial, all safety reporting will occur through this rollover trial, this includes the reporting of AEs that are unresolved from the parent trial, SAEs, and clinical events of special interest (AESIs).

A Safety Review Committee (SRC) will be reviewing emerging safety data at least every 16 weeks until the last enrolled subject in Group A has completed 28 d of follow-up. The SRC may then decide to decrease the frequency of its cumulative safety data reviews to a minimum of once a year. The SRC will also review data from Group B (e.g., SUSARS) on an as needed basis but also specifically data emerging from the Group B transplant subjects.

For a summary of the trial as a flow diagram, see the Schema in Section 1.2. For the planned assessments and visits, see the Schedule of Activities (SoA) in Section 1.3.

Duration of all trial periods

The planned trial duration for a subject in this trial is \sim 30 weeks (\leq 4 weeks of screening and \sim 26 weeks follow-up).

The estimated planned trial start (first subject enrolled) and trial end (last subject last visit) are JUN 2021 and Q4 2022.

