- m If applicable, Visit 7 or Visit 6 should be used to inform Group B transplant subjects (Cohort 13 of the BNT162-01 trial) on Dose 2 and informed consent must be collected. If Visit 6 is applicable, then Visit 7 must be skipped. Thereafter the SoA in Table 2a is applicable.
- n Record any non-trial SARS-CoV-2 vaccinations that trial subjects receive during the trial in the CRF until the last trial visit.
- o If a transplant subject consents to receive a second vaccination (i.e., 4th dose since the parent trial), the SoA in Table 2a is then applicable, there will be no blood sampling for CMI testing at the visit of consent (Visit 6 or Visit 7).
- p Only for Group B transplant subjects: record any non-trial SARS-CoV-2 vaccinations that trial subjects receive in the CRF.

Abbreviations: AE = adverse event; AESI = adverse event of special interest; CMI = cell mediated immunity; CRF = case report form; d = day; ELISA = enzyme-linked immunosorbent assay; EOT = end of trial; h = hour(s); IMP = investigational medicinal product; inj. = (IMP) injection; NAAT = nucleic acid amplification-based test; NATAB = neutralizing antibody titers and antibody binding; SAE = serious adverse event; SRC = safety review committee; SARS-CoV-2 = the virus leading to COVID-19; SoA = schedule of activities; WOCBP = women of childbearing potential.

BioNTech SE	Clinical Trial Protocol	Page 15 of 91 Version: 4.0
Confidential	BN1162-14	Date: 20 JAN 2022

Table 2a: Schedule of events for Immunology Subgroup of Group B transplant subjects (injection 2)

Activity	Visit 8	Visit 9	Visit 10	Visit 11 ^g	Visit 12 ^g	Early termination
Week(s) (post-Dose 2)		1	4	12	26	
Day (post-Dose 2)	1	8+2	29±7	85±10	182±20	
	(3 to 7 months post inj. 1; pre-dose except inj. 2)	(~7 d post inj. 2)	(~28 d post inj. 2)	(~3 months post inj. 2)	(~6 months post inj. 2 EOT Visit)	
Collect informed consent						
Assess inclusion/exclusion criteria compliance						
Collect demographic and medical history						
Physical examination	X ^a	X ^a			X a	X a
Vital signs, body weight ^b	X c					
Urine pregnancy test for WOCBP	Х					Х
Blood draw for hematology testing (up to 3 mL) $^{\rm d}$	Х	Х	Х			
Allocation to IMP						
IMP injection, then observe subjects for ~1 h	Х					
Subject hotline availability	=>	=>	=>	=>	End	(End)
Oral swab for NAAT-based SARS-CoV-2 testing for surveillance	×	х	х	х	Х	×
Oral swab for SARS-CoV-2 sequencing ^e	Х	Х	х	Х	Х	Х
Blood draws for NATAB and nucleocapsid protein testing (15 mL)	×	х	х	х	х	x

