from the BNT162-01 trial, transplant subjects demonstrate poor neutralizing antibody responses to SARS-CoV-2 Spike epitopes (Boyarsky et al. 2021; Sattler et al. 2021; Rincon-Arevalo et al. 2021), not unexpectedly, given the known poor antibody responses induced by influenza vaccines in solid organ transplant patients. Safety data from Cohort 13 subjects in the parent trial and a 3rd and 4th vaccination of Comirnaty in healthy volunteers supports evaluation of three or four vaccinations in the Cohort 13 transplant subjects (per communication of Data Monitoring Committee reviewing trial BNT162-02/CA4591001 [NCT04368728] Amendment 14). While high levels of neutralizing antibodies elicited by viral vaccines are known to protect in many other viral diseases, to date, the titer amount/level of neutralizing antibodies correlating with a decreased risk of SARS-CoV-2 infection nor a bone fide vaccine-induced functional correlate of protection has been determined/published. This trial will enable Cohort 13 transplant subjects to receive their first immunization in this trial as soon as three months after their second injection in the parent trial.

While monitoring transplant subject safety and reviewing immunogenicity data at 50 days after the third vaccination, an SRC decision was made to further evaluate the possibility of enhancing antibody response and monitoring the sustainability of antibody titers. The interim analysis post 50 days, using an evidence-based model (Khoury et al. 2021), demonstrated safety and protective efficacy (4-fold of convalescent) in up to 70% of the recipients. However, the response was inconsistent and heterogenous. There was also a limitation due to lack of CD4 counts or hypogammaglobulinemia information in low, negative, and/or inconsistent responders. Recently published evidence (Alejo et al. 2021) demonstrated that the fourth dose of vaccine in transplant recipients boosted immunologic response in low responders as well as non-responders. Another recently published data also from Kamar et al. 2021 suggested significant improvement of antibody titers 4 weeks after Dose 4 in solid organ transplant recipients who received the fourth dose 65 days after the third dose. Therefore, safety and efficacy data post-injection 2 in this trial will help support evidence-based rationale for the safety and efficacy of a 4th vaccination in this vulnerable population.

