3 OBJECTIVES AND ENDPOINTS

OBJECTIVES	ENDPOINTS	
Primary objectives	Endpoints	
To determine the safety and tolerability of one or two boosting doses of Comirnaty or one dose of BNT162b2s01 in BNT162-01 trial subjects, or two boosting doses of Comirnaty in BNT162-04 trial subjects.	 For all Group A and Group B subjects: The proportion of subjects in each treatment group with at least one SAE or the proportion of AESIs occurring up to 26 weeks after the first IMP injection. For Group A and a selected subset of Group B subjects: The frequency of solicited local reactions (pain, tenderness, erythema/redness, induration/swelling) at the injection site recorded up to 7 d after each IMP injection. The frequency of solicited systemic reactions (vomiting, diarrhea, headache, fatigue/tiredness, fever, chills, nausea, new or worsened muscle pain, new or worsening joint pain) recorded up to 7 d after each IMP injection. The proportion of subjects with at least one unsolicited TEAE occurring up to 28 d after IMP injection in each treatment group. 	
Secondary objectives	Endpoints	
To describe changes in SARS-CoV-2 neutralizing antibody titers from baseline to reference and SARS-CoV-2 variant B.1.351.	 For Group A and Group B subjects (except transplant subjects): Antibody titers to recombinant S1 and RBD protein derived from reference and SARS-CoV-2 variant B.1.351** will be assessed at baseline (Day 1) and then Day 8, Weeks 3*, 4, 7*, 12, and 26: Neutralizing antibody titers. Antibody titers (ELISA). SARS-CoV-2 functional cross-neutralization of variant B.1.351** to reference strain. *Group B only **Group B transplant subjects only: Antibody titers to recombinant S1 and RBD protein derived from SARS-CoV-2 will be assessed at baseline (Day 1) and then Day 8, Weeks 4, 12, and 26 post Dose 1, and at Dose 2 (Day 1) and then Day 8, Weeks 4, 12, and 26 post Dose 2: Neutralizing antibody titers. Antibody titers (ELISA). 	
Exploratory objectives	Endpoints	

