6 TRIAL TREATMENTS

Trial treatment is defined as any investigational treatment(s), marketed product(s), intended to be administered to a trial subject according to the trial protocol.

IMP name:	BNT162b2 (Comirnaty) or BNT162b2s01.
Туре:	Vaccine (BNT162 RNA-LNP vaccine utilizing modRNA).
Administration route:	Intramuscular (IM); upper arm, musculus deltoideus. The same arm may be used for both immunizations. The non-dominant arm is preferred.
Dosing regimen:	Group A: One (at Day 1) IM injection with 30 µg of either Comirnaty or BNT162b2s01.
	Group B: Two (at Day 1 and Day 21) IM injections with 30 μg of Comirnaty, except Group B transplant subjects.
	Group B transplant subjects: Two IM injections of 30 µg of Comirnaty, with injection 2 administered 3 to 7 months after injection 1 (Day 1).
	The planned time points for injection of IMP for Groups A and B are provided in the SoA (Section 1.3).
Sourcing:	Provided centrally by the sponsor.
Packaging and labeling:	IMP will be provided in glass vials as open-label supply. Each vial will be labeled as required per country requirements. For details, see the Pharmacy Manual.

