10.3.1 Definition of AE and TEAE

- An AE is any untoward medical occurrence in a trial subject, temporally associated with the use of trial treatment, whether or not considered related to the IMP.
 NOTE: An AE can therefore be any unfavorable and unintended sign (including an abnormal laboratory finding that is clinically significant), symptom, or disease (new or exacerbated) temporally associated with the use of IMP.
- Events after signing ICF and before IMP administration will be handled as AEs (also called pre-existing conditions).
- A TEAE is defined as any AE with an onset after the first IMP injection or worsened after the first IMP injection (if the AE was present before the first administration of IMP). AEs with an onset date more than 28 d after the last administration of IMP will be considered as treatment-emergent only if assessed as related to IMP by the investigator.

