6.1.1. Tables and listings

Tables

In general, data will be summarized as follows:

- Group A by vaccine [Comirnaty[®], BNT162b2s01], and total
- Group A subjects having received Comirnaty[®] by HIV infection status
- Group A subjects having received BNT162b2s01 by HIV infection status
- Group B by transplant status, and total
- Group B immunology subset by transplant status, and total

Descriptive summary tables and figures will be based on scheduled visits.

Continuous variables will be summarized using the following descriptive statistics: number of subjects with non-missing data (n), mean, standard deviation (SD), median, minimum (min) and maximum (max).

Descriptive statistics of titer and fold rise of titer will additionally include geometric mean and its two-sided 95% confidence interval (CI). The geometric mean titer (GMT) is calculated as the mean of the logarithm of the functional antibody titers, backtransformed into the original scale. Two-sided CIs will be obtained by calculating CIs using t-distribution for the mean of the logarithmically transformed assay results and transforming the limits back to the original scale.

Geometric mean fold rise (GMFR) is calculated as the mean of the difference of logarithmically transformed assay results (post vaccination time point – pre vaccination time point) and back-transformed into the original scale. Two-sided CIs will be obtained by calculating CIs using Student's t-distribution for the mean difference of the

logarithmically transformed assay results and transforming the limits back to the original scale.

Categorical variables will be summarized presenting absolute and relative frequencies (n and %) of subjects in each category (including the category 'missing' if applicable). Percentages will be calculated based on the number of subjects in the respective analysis set (N) as denominator if not stated differently. Percentages may be presented with exact 95% Clopper-Pearson CIs.

SDs and CIs will only be calculated if values from at least 3 subjects are available.

Listings

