6.4. Primary endpoint analyses

The primary endpoints are solicited local reactions at the injection site occurring up to 7 days after each injection, solicited systemic reactions occurring up to 7 days after each injection, the proportion of subjects with at least one serious adverse event (SAE) occurring up to 26 weeks after the first injection, the proportion of subjects with at least one adverse event of special interest (AESI) occurring up to 26 weeks after the first injection and the proportion of subjects with at least one unsolicited treatment emergent adverse event (TEAE) occurring up to 28 days after each injection.

All primary analyses will be performed using the SAF and analyses of adverse events for Group B will possibly be repeated using the SAFB.

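### For transplant subjects the primary SAE/AESI window ends 26 weeks after injection 1, so it covers about half of the follow-up after injection 2 at most, and none once injection 2 falls later than about 6 months

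*Protocol*

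**What the plan says.** - **Primary endpoint.** Protocol section 3, for all Group A and Group B subjects, takes the proportion with an SAE, or "the proportion of AESIs occurring up to 26 weeks after the first IMP injection". SAP Table 2 repeats this. SAP 6.4 names "the proportion of subjects with at least one serious adverse event (SAE) occurring up to 26 weeks after the first injection" and gives AESIs the same limit.
- **A second window.** SAP 6.4.3 says that AESIs and SAEs are evaluated for 26 weeks from signature of the consent form, in all groups.
- **Dosing of transplant subjects.** Protocol section 6 gives two injections, "with injection 2 administered 3 to 7 months after injection 1 (Day 1"). Under footnote m of protocol Table 2, consent for injection 2 is taken at Visit 6 (Day 85±10) or Visit 7 (Day 182±20).
- **Follow-up after injection 2.** Table 2a runs to Visit 12, Day 182±20 after injection 2, labelled "6 months post inj. 2 EOT Visit". Its footnote f keeps SAE and AESI recording open to the end of trial.
- **Treatment-emergent events.** Protocol 10.3.1: "AEs with an onset date more than 28 d after the last administration of IMP will be considered as treatment-emergent only if assessed as related". The investigator makes that judgement. SAP 6.4.3 gives transplant subjects a 28-day interval after injection 2.
- **Purpose.** Protocol 2.2 states that "safety and efficacy data post-injection 2 in this trial will help support evidence-based rationale for the safety and efficacy of a 4th vaccination" in these subjects.
- **Denominator.** SAP 6.1.1: "Percentages will be calculated based on the number of subjects in the respective analysis set (N) as denominator if not stated differently". It also says that some adverse-event analyses will be rerun for Group B on the safety boost set (SAFB, subjects with two doses) if that set differs from the safety set. SAP 6.4 makes the rerun only a possibility.
- **Duration.** Protocol synopsis: "The planned trial duration for a subject in this trial is" about 30 weeks. SAP 1.2 agrees. Neither separates out transplant subjects.

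**The concern.** For other Group B subjects the endpoint fits the schedule. Injection 2 falls at about Day 22, and Day 182 is both the end of the window and the last visit. Transplant subjects are on a different schedule, and the endpoint was not adapted to it. Their SAE/AESI proportion mixes the months after injection 1 with a variable, sometimes empty, slice of the time after injection 2.

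The primary objective covers the safety of one or two doses, and the rationale says that post-injection-2 data will inform the safety of a 4th vaccination. The SAE/AESI component of the primary endpoint is a poor instrument for that. Part or all of the follow-up after the dose in question lies outside it, although the events are collected.

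**Working it through.** The plan states no figure for this coverage, so there is none to reproduce. The check is date arithmetic.

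**Inputs.** Window: 26 × 7 = 182 d from injection 1 (protocol section 3, SAP 6.4). Injection 2 at m = 3 to 7 months (protocol section 6). Follow-up after injection 2: 182 d (Table 2a, Visit 12). Month: 30.25 d (SAP 6.1.2). Screening: up to 30 d (Visit 0, Day -30 to -1). Transplant subjects: up to 15 (protocol 4.1).

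**Coverage, first-injection anchor.** Covered days = max(0, 182 − 30.25m); share = covered days / 182.

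**Coverage, consent anchor with s = 30 d of screening.** Covered days = max(0, 182 − 30 − 30.25m).

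| Injection 2 at | Days after injection 1 | Covered, SAP 6.4 | Covered, SAP 6.4.3 |
|---|---|---|---|
| 3 months | 90.75 | 91.25 d (50.1%) | 61.25 d (33.7%) |
| 4 months | 121.00 | 61.00 d (33.5%) | 31.00 d (17.0%) |
| 5 months | 151.25 | 30.75 d (16.9%) | 0.75 d (0.4%) |
| 6 months | 181.50 | 0.50 d (0.3%) | 0 d |
| 7 months | 211.75 | 0 d | 0 d |

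At 7 months the first-injection window closed 211.75 − 182 = 29.75 d before injection 2. Coverage reaches zero at 182 / 30.25 = 6.02 months.

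**Sensitivity to month length.** The 3-month share is 49.8% with 365.25/12 d, 50.5% with 30 d and 53.8% with 28 d. The conclusion does not depend on the convention.

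**Zero or near-zero coverage is a planned route.** If consent for injection 2 is taken at Visit 7, the earliest day is 162. That leaves about 20 d of the window even if injection 2 follows at once.

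**Tracing one event.** Take injection 2 at 5 months and an unrelated SAE 60 d later, which is 151.25 + 60 = 211.25 d after injection 1.
- Primary SAE proportion: out, since 211.25 > 182.
- 28-day interval after injection 2: out, since 60 > 28.
- All-TEAE and treatment-emergent SAE tables: out, because the event is unrelated and began more than 28 d after the last injection.
- SAE and AESI summaries in SAP 6.4.3: out, if the 26-week sentence in that section governs them.
- Any AE: in. Grade ≥3 AE and Deaths: in, if the event qualifies.

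**Denominator.** If k of 15 transplant subjects receive injection 2 and e of them have an event in an interval after it, the safety set gives e/15 and the recipients give e/k. The first is k/15 of the second. The documents do not give k. For k from 5 to 15 (assumption) the factor runs from 0.33 to 1. With k = 10 and e = 2 (assumption) it is 13.3% against 20.0%. SAP 1.2 expects some subjects not to receive this dose.

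**Duration from Day 1.** (90.75 + 182) / 7 = 39.0 weeks; (211.75 + 182) / 7 = 56.25 weeks. About 4 weeks of screening makes this roughly 43 to 60 weeks, against about 30 stated.

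**The case against.** The other side has a good deal to say.

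- **Other primary endpoints follow injection 2.** Solicited local and systemic reactions are assessed for 7 days after each injection, and unsolicited TEAEs for 28 days. A reader might infer that the primary safety assessment as a whole reflects only the first dose. The documents do not support that; the gap is in the SAE/AESI component.
- **Late events do not vanish.** A reader might infer that a late unrelated SAE enters no planned proportion. SAP 6.4.3 also summarises Any AE, Grade ≥3 AE and Deaths for all groups, with no stated cut-off. A late event judged related is still a TEAE. Collection continues to Visit 12, and the Safety Review Committee looks specifically at transplant data.
- **The denominator is partly handled.** SAP 6.1.1 says that some adverse-event analyses will be rerun on the SAFB when the sets differ. Solicited reactions use subjects with diary data in the interval, so they are not diluted.
- **The trial is descriptive and the group is small.** No hypothesis is tested, and at most 15 of up to 549 subjects (90 + 459) are affected.

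All of this stands, and it limits the point. It does not close it: the only windows given for the SAE and AESI proportions stop before most or all of the follow-up after injection 2, and the two windows disagree. The SAP does not say which adverse-event analyses will be rerun on the SAFB, and its two statements on the rerun differ in force. The consent sentence might be read as meaning the second consent that transplant subjects give for injection 2, but it is worded for all groups and does not say so.

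An average coverage across the 3-to-7-month range is also tempting. It would need a distribution of injection times that the documents do not give. Consent at Visit 6 or Visit 7 suggests clustering near the two ends of the range, so only the range is reported here.

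**Conclusion.** The point holds for the SAE/AESI component of the primary endpoint in Group B transplant subjects. Under the first-injection anchor the window covers 50.1% of the 182 days after injection 2 at best, and nothing after about 6 months. Under the consent anchor in SAP 6.4.3 with 30 days of screening, the best case is 33.7%. These figures rest on the SAP's month length and on nominal visit days.

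A shorter window, or a denominator that includes subjects without injection 2, can only lower an at-least-one-event proportion or leave it unchanged. With 15 subjects, one omitted subject with an event is 1/15 = 6.7 percentage points. A reader might infer that the plan makes the 4th vaccination look safer overall. That is not shown, because the other endpoints and summaries do include time after injection 2.

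This should be fixed, but it does not threaten the trial: the fault lies in endpoint and analysis wording, and no data are lost.

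**What to change.** 1. In protocol section 3 (and the synopsis), SAP Table 2, SAP 6.4 and SAP 6.4.3, define the SAE/AESI endpoint for Group B transplant subjects as events up to 26 weeks after each IMP injection. Report two periods separately: from injection 1, censored at injection 2, and from injection 2 (Visit 8 to Visit 12).
2. Replace the consent anchor in SAP 6.4.3 so that it agrees with the first-injection anchor in protocol section 3 and SAP 6.4.
3. For adverse-event, SAE and AESI intervals after injection 2, use the transplant subjects in the SAFB as the denominator. Make SAP 6.1.1 and SAP 6.4 agree on whether the SAFB analyses will be done, and list which ones. Solicited reactions need no change.
4. In the protocol synopsis and SAP 1.2, state the planned duration for transplant subjects who receive injection 2 as about 39 to 56 weeks after Day 1, plus screening.

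The cost is endpoint and SAP wording plus one more table. Table 2a already collects the events to Visit 12, so no new visit, sample or data item is needed and dosing is unaffected.
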